7.2 Initial Phase visit (only for applicable subjects)

(-2 to 0 weeks relative to Randomization (baseline) visit)

1. Dispense instruction and material for Standard-of-Care
2. Record of Adverse Events
3. Record changes on concomitant medication(s)

7.3 Randomization visit

(Day 0)

1. Re-confirm eligibility of subject
2. Ulcer evaluation
3. Vital signs
4. Perform physical examinations
5. Obtain blood samples for hematologic and biochemical tests (The tests can be waived if the tests have been performed within past 28 days)
6. Assign randomization number to eligible subject
7. Record changes on concomitant medication(s)
8. Dispense material of standard-of-care
9. Record adverse event(s)
10. Dispense trial medication
11. Dispense diary to patient

7.4 Evaluation visits during treatment period in visits 4 to 11

(Weeks 1, 2, 3, 4, 6, 8, 10, 12 with time window ± 4 days)

Subjects confirmed complete ulcer closure before week-12 visit will be arranged for post-treatment follow-up.

1. Ulcer evaluation
2. Vital signs
3. Perform physical examinations
4. Obtain blood samples for hematologic and biochemical tests (will only be performed at week 12 visit or when subject complete the treatment period)
5. Record changes on concomitant medication(s)
6. Dispense material of standard-of-care

7. Record adverse event(s)
8. Collect unused treatment medication(s) (which is dispensed at prior visit)
9. Dispense trial medication (excluding week 12 visit)
10. Collect and check diary (which recorded from previous visit)
11. At week-12 visit only, perform pregnancy test for female with childbearing potential

7.5 Follow-up visits

The follow-up visits will be performed at 2, 4, and 8 weeks after for subjects achieving confirmed complete ulcer closure during treatment period and at 2 weeks after treatment period (week 14 or visit 12) only for those not.

(The visit day will be week 14 for visit 12, week 16 for visit 13, and week 20 for visit 14, each with time window ± 4 .)

1. Ulcer evaluation
2. Vital signs
3. Perform physical examinations
4. Record changes on concomitant medication(s)
5. Record adverse event(s)

7.6 Final visit

The final visit will be performed at 12 weeks ± 4 days after confirmation of complete ulcer closure for subjects achieved and at visit 13 (week 16 ± 4 days) for those not.

1. Ulcer evaluation
2. Vital signs
3. Perform physical examinations
4. Record changes on concomitant medication(s)
5. Record adverse event(s)
6. Complete an exit form in the case report form and dismiss the subject

8. ADVERSE EVENTS

8.1 Definitions

- *Adverse Event (AE):*

An AE is any untoward medical occurrence in a patient or clinical investigation participant administered a study medication and that does not necessarily have a causal relationship with this treatment. An AE can therefore be any unfavorable and unintended sign, symptom, or disease temporally associated with the use of a study medication, whether or not related to the study medication. Laboratory abnormalities should not be recorded as AEs unless determined to be clinically significant by the Investigator.

- *Expected AE:*

Expected AE are defined as any event, the specificity or severity of which is consistent with the current investigator brochure or other technique documents.

- *Unexpected AE:*

Unexpected AE is defined as any event, the specificity or severity of which is not consistent with the current investigator brochure or other technique documents. "Unexpected", as used in this definition, refers to an adverse drug experience that has not been previously observed (e.g., included in the investigator brochure) rather than from the perspective of such experience not being anticipated from the pharmacological properties of the pharmaceutical product.

- *Serious Adverse Event (SAE):*

Serious Adverse Event (SAE): A Serious Adverse Event is defined as an AE meeting one of the following conditions:

- Death during the period of protocol defined surveillance
- Life Threatening Event (defined as a participant at immediate risk of death at the time of the event)
- An event requiring inpatient hospitalization or prolongation of existing hospitalization during the period of protocol defined surveillance
- Results in congenital anomaly or birth defect
- Results in a persistent or significant disability/incapacity
- Based upon appropriate medical judgment, the event may jeopardize the participant and may require medical or surgical intervention to prevent one of the outcomes listed above.

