8.3.2 Reporting of AE

Serious, alarming and/or unusual adverse events must be reported to the Sponsor/CRO contact within 24 hours of the investigator's knowledge of the event. Any event requiring hospitalization (or prolongation of hospitalization) that occurs during the course of a subject's participation in a clinical study must be reported as a serious adverse event, except hospitalizations for the following:

- Social reasons in absence of an adverse event
- Surgery or procedure planned before entry into the study (must be documented in the CRF)

The investigator is responsible to communicate details of medical emergencies in trial subjects to the Ethics Committee. Sponsor is responsible to inform the events to the regulatory authorities.

Fatal or life-threatening, unexpected ADRs should be notified to Taiwan National ADR Reporting Center by sponsor/CRO as soon as possible, but no later than 7 calendar days, after first acknowledged by the investigator, and a complete report should be followed 8 additional calendar days. This report must include an assessment of the importance and implication of the findings and/or previous experience on the same or similar medical products. Serious, unexpected ADRs that are not fatal or life-threatening must be filed as soon as possible but no later than 15 calendar days after first acknowledged by the investigator that a case qualifies.

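### The Expected and Unexpected AE definitions in Section 8.1 overlap: an event that matches the brochure on only one of type and severity meets both, so a serious reaction could be misclassified and not expedited

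*Combined protocol and SAP*

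**What the plan says.** Section 8.1 defines two classes by how an event compares with the investigator brochure or other technical documents. For the first: "Expected AE are defined as any event, the specificity or severity of which is consistent with the current investigator brochure or other technique documents". For the second: "Unexpected AE is defined as any event, the specificity or severity of which is not consistent with the current investigator brochure or other technique documents". An explanatory sentence follows the second definition. It says that the term "refers to an adverse drug experience that has not been previously observed", gives inclusion in the brochure as its example, and contrasts this with whether the pharmacology would have led one to anticipate the event. It does not mention severity.

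Section 8.3.2 then uses the classification. The faster report reads: "Fatal or life-threatening, unexpected ADRs should be notified to Taiwan National ADR Reporting Center by sponsor/CRO as soon as possible", and "no later than 7 calendar days". The slower one reads: "Serious, unexpected ADRs that are not fatal or life-threatening must be filed as soon as possible but no later than 15 calendar days". Separately, the same section requires serious, alarming or unusual events to reach the sponsor or CRO within 24 hours of the investigator learning of them, with no reference to expectedness.

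**The concern.** Expected and unexpected are meant to be opposites, so each event should fall in exactly one class. When two attributes are compared, the opposite of at least one being inconsistent is that both are consistent. Section 8.1 instead calls an event expected when either attribute is consistent. An event that matches on one attribute and not on the other therefore belongs to both classes.

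The case of interest is a reaction of a type the brochure lists, occurring at a severity it does not describe. It is expected by type and unexpected by severity. Two assessors who each follow the text can class the same event in opposite ways. If it is also a serious adverse drug reaction, the class decides whether anyone starts a 7-day or 15-day clock. Section 8.2 requires an intensity grade for every AE, so the severity mismatch would be on record, yet one of the two definitions lets it be passed over.

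**Working it through.** No sample size, power or event count is involved, and the plan gives no figure to reproduce. The check is a truth table on the wording.

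**Inputs.** Let S mean that the specificity (type) of the event is consistent with the brochure, and V that its severity is consistent. From Section 8.1:

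- Expected = S or V
- Unexpected = (not S) or (not V)

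| Type consistent (S) | Severity consistent (V) | Expected | Unexpected | Class |
|---|---|---|---|---|
| yes | yes | yes | no | expected only |
| yes | no | yes | yes | both |
| no | yes | yes | yes | both |
| no | no | no | yes | unexpected only |

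**Result as written.** Two of the 4 combinations fall in both classes and none falls in neither. A listed reaction at greater severity is the second row. The third row matters less: where the brochure does not list a type of event, it will normally give no severity for that event to match.

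**Link to reporting.** Section 8.3.2 needs two conditions for an expedited report: the reaction is unexpected, and it is either fatal or life-threatening (7 days) or otherwise serious (15 days). It does not use the term expected and contains no clause removing reactions that are also expected. A serious reaction in the second row is unexpected, so the literal rule requires the report.

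**Does the explanatory sentence settle the overlap?** It can be read in two ways. If what must not have been observed before is the type of event, a listed type has been observed and the event leans towards expected. If it is the event at that severity, a life-threatening form of something listed only as mild has not been observed, and the event is unexpected. The sentence does not say which is meant. Section 8.2 does not help: its text on expected events related to the disease process is a different concept and is still an unfilled template instruction.

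**Possible wording changes, checked on the same table.**

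- 'And' in the Expected definition only: Expected = S and V; Unexpected is unchanged. Combinations in both classes: 0 of 4; in neither: 0 of 4. The second row becomes unexpected only.
- 'And' in both definitions: Unexpected becomes (not S) and (not V). The two mixed rows then fall in neither class: 2 of 4 unclassified.
- 'And' in the Unexpected definition only: the classes are complements, but the second row becomes expected only and drops out of the expedited rule.

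Only the first removes the overlap and keeps the reports that Section 8.3.2 now requires.

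**The case against.** The strongest reply is that the reporting rule does not use the faulty definition. Section 8.3.2 turns on unexpected, and the first sentence of that definition works on its own: inconsistency in either attribute is enough. Expected AE drives no visible reporting rule. A reader might infer that the protocol permits a worse-than-listed reaction to be filed as expected and left unexpedited. The documents do not support that, because nothing exempts a reaction that meets both definitions. This part of the reply stands in full.

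Three further points also have weight. The sponsor or CRO, which makes the 7-day notification, hears of every serious event within 24 hours whatever its class. The explanatory sentence seems aimed at stopping pharmacological predictability from making an event expected, which widens the unexpected class; it does not withdraw the severity criterion in the sentence before it. And two of four counts logical combinations, not events. The brochure is not among the documents, so how many reactions it lists, and at what severity, is unknown.

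These points shrink the concern but do not remove it. The 24-hour rule brings the event to the party that must then apply the same two conflicting definitions. The literal reading gives the right answer only if the assessor disregards an express definition under which the event is expected, and no visible text tells the assessor to do so.

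**Conclusion.** The definitions are wrong as written: they are internally inconsistent, and 2 of 4 combinations fall in both classes, one of which is likely to matter. The severity is minor. An expedited report could be missed through misclassification, but the written rule does not excuse missing it. The exposure is limited to reactions that are serious, are judged drug-related, and match the brochure on one attribute only. The documents give no basis for estimating how many there would be.

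The conclusion rests on the wording of Sections 8.1 and 8.3.2, which are not redacted at these points, and on the assumption that no redacted text ranks the two classes. Sample size and efficacy analysis are not affected.

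**What to change.** 1. In the Expected AE definition only, replace 'or' with 'and' between specificity and severity.
2. Leave the first sentence of the Unexpected AE definition as it is.
3. Reword the explanatory sentence so that an experience counts as not previously observed when the current brochure does not list it at the observed specificity and severity. The contrast with pharmacological anticipation can stay.

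The cost is one word and one clause in a protocol amendment, which goes to the IRB under Section 11.2. Read literally, Section 8.3.2 already requires the reports in question, so the change adds no reporting duty. It makes the existing one unambiguous for whoever classifies the event.

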8.2 AE/SAE Intensity and Relationship Assignment

- AE/SAE Intensity

The investigator must rate the intensity for all AEs that occur during the study using the grades provided below:

- Grade 1 (Mild): events require minimal or no treatment and do not interfere with the subject's daily activities.

- Grade 2 (Moderate): events result in a low level of inconvenience or concern with the therapeutic measures. Moderate events may cause some interference with functioning.
- Grade 3 (Severe): events interrupt a subject's usual daily activity and may require systemic drug therapy or other treatment. Severe events are usually incapacitating.
- Grade 4 (Life threatening): Any adverse drug experience that places the subject or participant, in the view of the investigator, at immediate risk of death from the reaction as it occurred, i.e., it does not include a reaction that had it occurred in a more severe form, might have caused death.
- Grade 5 (Death)

- AE/SAE Relationship Assessment

The investigator will be asked to assess all AEs with respect to their causal relationship to the study drug according to the following classification:

- Definitely Related: There is clear evidence to suggest a causal relationship, and other possible contributing factors can be ruled out. The clinical event, including an abnormal laboratory test result, occurs in a plausible time relationship to study agent/intervention administration and cannot be explained by concurrent disease or other drugs or chemicals. The response to withdrawal of the study agent/intervention (dechallenge) should be clinically plausible. The event must be pharmacologically or phenomenologically definitive, with use of a satisfactory rechallenge procedure if necessary.
- Probably Related: There is evidence to suggest a causal relationship, and the influence of other factors is unlikely. The clinical event, including an abnormal laboratory test result, occurs within a reasonable time sequence to administration of the study agent/intervention, is unlikely to be attributed to concurrent disease or other drugs or chemicals, and follows a clinically reasonable response on withdrawal (dechallenge). Rechallenge information is not required to fulfill this definition.
- Possibly Related: There is some evidence to suggest a causal relationship (e.g., the event occurred within a reasonable time after administration of the trial medication). However, the influence of other factors may have contributed to the event (e.g., the subject's clinical condition, other concomitant events). Although an adverse drug event may rate only as "possible" soon after discovery, it can be flagged as requiring more information and later be upgraded to probable or certain as appropriate.
- Unlikely: A clinical event, including an abnormal laboratory test result, whose temporal relationship to study agent/intervention administration makes a causal relationship improbable (e.g., the event did not occur within a reasonable time after administration of the trial medication) and in which other drugs or chemicals or underlying disease provides plausible explanations (e.g., the subject's clinical condition, other concomitant treatments).
- Not related: The AE is completely independent of study agent/intervention administration, and/or evidence exists that the event is definitely related to

another etiology. There must be an alternative, definitive etiology documented by the clinician Expected Events Related to Disease Process: Provide explicit definitions of the type(s), grade(s), and duration(s) of adverse event(s) that will be considered disease related.

8.3 Collecting, Recording and Reporting of Adverse Events

8.3.1 Collecting and Recording of AE

AEs may be volunteered spontaneously by the study subject, discovered as a result of general questioning by the study staff, or determined by physical examination. All AEs starting from signing ICF will be recorded on the CRF. For all AEs, the investigator must pursue and obtain adequate information both to determine the outcome of the AE and to assess whether it meets the criteria for classification as a serious AE requiring immediate notification. Follow-up of the AE, even after the date of study drug discontinuation, is required if the AE persists. The study subject will be followed until the event resolves or stabilizes at a level acceptable to the investigator. For patients receiving hemodialysis, taking regular arteriovenous fistula will not be considered as an AE.

8.3.2 Reporting of AE

Serious, alarming and/or unusual adverse events must be reported to the Sponsor/CRO contact within 24 hours of the investigator's knowledge of the event. Any event requiring hospitalization (or prolongation of hospitalization) that occurs during the course of a subject's participation in a clinical study must be reported as a serious adverse event, except hospitalizations for the following:

- Social reasons in absence of an adverse event
- Surgery or procedure planned before entry into the study (must be documented in the CRF)

The investigator is responsible to communicate details of medical emergencies in trial subjects to the Ethics Committee. Sponsor is responsible to inform the events to the regulatory authorities.

Fatal or life-threatening, unexpected ADRs should be notified to Taiwan National ADR Reporting Center by sponsor/CRO as soon as possible, but no later than 7 calendar days, after first acknowledged by the investigator, and a complete report should be followed 8 additional calendar days. This report must include an assessment of the importance and implication of the findings and/or previous experience on the same or similar medical products. Serious, unexpected ADRs that are not fatal or life-threatening must be filed as soon as possible but no later than 15 calendar days after first acknowledged by the investigator that a case qualifies.

9. DATA ANALYSIS

9.1 Data Quality Assurance

The sponsor will provide paper CRFs or electronic CRFs (via Electronic Data Capture (EDC) system) for the recording and collection of subject data and for the collection of data. All CRFs will be completed as soon as possible after the subject's visit. Corrections to data on the CRFs will be documented or traced. The investigator will review CRFs to indicate that, to his/her knowledge, they are complete and accurate. If further changes are made after this, the investigator will need to again sign the investigator signature page or approve electronically. Designated source documents will be signed and dated by the appropriate study personnel.

9.2 Clinical Data Management

The investigator must agree to complete and maintain source documents and CRFs for each subject participating in the study.

The sponsor/CRO will be responsible for the processing and quality control of the data. Data management will be carried out as described in the sponsor/CRO's standard operating procedures (SOPs) for clinical studies.

The handling of data, including data quality control, will comply with regulatory guidelines and the sponsor/CRO's SOPs as well as provisions of the study-specific Data Management Plan.

10. SAMPLE SIZE AND STATISTICAL METHODS

10.1 Determination of Sample Size

[REDACTED]

[REDACTED]

10.2 Statistical and Analytical Plans

10.2.1 Analysis Population

Three data sets will be introduced for statistical analysis.

Intent-to-treat (ITT) population:

- All randomized subjects who have received at least one dose study medication.

Per-protocol (PP) population:

- A subset of ITT population
- Fulfill all inclusion and exclusion criteria
- Dosed with at least 8 weeks study drug or with early confirmed complete ulcer closure AND with at least 70% treatment compliance
- Did not receive any prohibited treatment during treatment period
- With any post-treatment assessment relevant to efficacy endpoint up to end of dosing period

Efficacy endpoints will be analyzed on ITT and PP population. Demographics, baseline characteristics, and safety endpoints will be analyzed on ITT population. The conclusion of efficacy will be made according to the results of ITT population analysis.

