5.2 Storage and Drug Accountability

Adequate supplies of either CSTC1 or CSTC1 matched vehicle will be packaged for one visit dispense. The total number of tubes of investigational product planned for each subject will be 100 and each subject is expected to use at most 1 tube per day. Each subject will be dispensed for up to 8 visits at visits 3 to 10. At each visit of visits 3 to 9, investigational product should be supplied to the subject for use based on the number of tubes of unused investigational product the subject possesses and to the extent of date that the subject may return with remaining eligible for next visit. Therefore, the number of tubes supplied at each visit will be calculated as (date of subject expected to return for next visit – date of current visit + 4 days of time window - number of tubes the subject possesses).

The trial medication for both treatment groups will be packaged in an identical way. Drug accountability will be recorded for the weight of test drug given to the subjects and returned to site by the subjects. Subject will be dispensed diary cards to record the times in each day they apply the study medications to the treated area.

All the products should be stored at room temperature (under 30° C) and be managed by the hospital pharmacies.

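### The set called ITT, which decides efficacy, is a modified ITT that depends on receipt of a dose, and the visible text lets a site document that dose only through diaries and product returned from visit 4 on

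*Combined protocol and SAP*

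**What the plan says.** Section 10.2.1 (repeated in the Protocol Summary) defines the ITT set as "All randomized subjects who have received at least one dose study medication". The same section states: "The conclusion of efficacy will be made according to the results of ITT population analysis". It uses the same set for safety: "Demographics, baseline characteristics, and safety endpoints will be analyzed on ITT population". It announces that "Three data sets will be introduced for statistical analysis" but defines only two, ITT and per-protocol (PP). The PP set requires, among other things, "With any post-treatment assessment relevant to efficacy endpoint up to end of dosing period"; the ITT set has no such requirement.

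On how a first dose becomes known:

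- Section 7.3 lists "Dispense trial medication" and dispensing of a diary at the randomization visit. It lists no supervised first application.
- Section 5.2 says: "Subject will be dispensed diary cards to record the times in each day they apply the study medications to the treated area". Accountability is by weight of product given out and weight brought back.
- Section 7.4 has the site "Collect and check diary (which recorded from previous visit") and collect unused product at visits 4 to 11. The Schedule of Assessments agrees: diary return and the count of returned medication both start at visit 4 (week 1).

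Section 5.3 (dose regimen) is redacted, as are most of section 5.4 (compliance), section 10.1 (sample size) and the efficacy-analysis text in section 10.2.2.

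**The concern.** A randomized-and-dosed set does little harm when the first dose is observed for everyone, because membership is then settled by a recorded fact at the start. Here the visible text gives no such record. For a subject who is randomized, leaves with product and never returns, neither diary nor tubes reach the site. Someone must then decide, without that evidence, whether the subject belongs in the set that carries the efficacy conclusion.

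If receipt is read as documented application, exclusion follows early dropout, which treatment can influence (for example through local intolerance). The comparison would then no longer be protected by randomization. The vehicle arm is small, about 25 of 125 at 4:1, so one or two membership decisions visibly move the control rate. Section 2.1.2 says the study is meant for registration, so the deciding set should not depend on an undefined term.

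**Working it through.** **1. The readings of receiving a dose, for a subject who never returns after visit 3**

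| Reading | Member of ITT? | Can the site verify it from the visible procedures? |
|---|---|---|
| Product was dispensed | Yes | Yes, at visit 3 |
| Product was applied | Yes, if applied once | Not from diary or tubes |
| Application is documented | No | The lack of a record is itself the exclusion |

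No visible text chooses between them. Only the third reading removes early dropouts as such.

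**2. The plan's own figure**

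Section 3.1 gives about 125 recruited for 100 PP-evaluable subjects (80 versus 20). 100/(1 − 0.20) = 125, but the 20% is back-solved from 1 − 100/125, so this is not an independent check. The 80 versus 20 cannot be reproduced because closure rates and power are redacted.

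**3. Illustration**

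Inputs from the plan: 125 subjects at 4:1, so 125 × 4/5 = 100 CSTC1 and 125/5 = 25 vehicle; CMH test; alpha 0.05 (two-sided assumed). Assumed: all closure counts and all numbers lost before visit 4. Subjects lost this way have no closure, so excluding them changes only the denominators.

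Single-stratum CMH, 1 df, no continuity correction. With a closures of n₁ on CSTC1, c of n₂ on vehicle, N = n₁ + n₂ and m = a + c:

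E = n₁m/N; V = n₁n₂m(N − m)/[N²(N − 1)]; Q = (a − E)²/V.

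Worked case, 60/100 versus 9/25: m = 69, E = 100 × 69/125 = 55.2, V = 4.986, Q = 4.8²/4.986 = 4.62, p = 0.032. With two vehicle subjects excluded, 60/100 versus 9/23: E = 100 × 69/123 = 56.10, V = 4.643, Q = 3.28, p = 0.070.

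| Excluded (CSTC1, vehicle) | CSTC1 | Vehicle | Difference (points) | p |
|---|---|---|---|---|
| none | 60/100 = 60.0% | 9/25 = 36.0% | 24.0 | 0.032 |
| 4, 1 | 60/96 = 62.5% | 9/24 = 37.5% | 25.0 | 0.027 |
| 8, 2 | 60/92 = 65.2% | 9/23 = 39.1% | 26.1 | 0.023 |
| 12, 3 | 60/88 = 68.2% | 9/22 = 40.9% | 27.3 | 0.019 |
| 10, 0 | 60/90 = 66.7% | 9/25 = 36.0% | 30.7 | 0.006 |
| 0, 2 | 60/100 = 60.0% | 9/23 = 39.1% | 20.9 | 0.070 |
| none | 50/100 = 50.0% | 6/25 = 24.0% | 26.0 | 0.020 |
| 4, 1 | 50/96 = 52.1% | 6/24 = 25.0% | 27.1 | 0.018 |
| 8, 2 | 50/92 = 54.3% | 6/23 = 26.1% | 28.3 | 0.016 |
| 12, 3 | 50/88 = 56.8% | 6/22 = 27.3% | 29.5 | 0.014 |
| 10, 0 | 50/90 = 55.6% | 6/25 = 24.0% | 31.6 | 0.005 |
| 0, 2 | 50/100 = 50.0% | 6/23 = 26.1% | 23.9 | 0.039 |
| none | 52/100 = 52.0% | 8/25 = 32.0% | 20.0 | 0.075 |
| 4, 0 | 52/96 = 54.2% | 8/25 = 32.0% | 22.2 | 0.049 |

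Exclusions in the 4:1 ratio add 1.0 to 3.5 points. Ten on CSTC1 only add 5.6 to 6.7 points. Two on vehicle only subtract 2.1 to 3.1 points. The result crosses 0.05 in one direction in the 60/9 example (0, 2) and in the other in the 52/8 example (4, 0).

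**The case against.** A reader might infer that the first dose is applied at home and that subjects who never return therefore leave the analysis instead of counting as failures. The documents do not support that.

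- **Place of the first dose.** No visible text states it. An item missing from a short visit list supports an inference only, and the redacted sections 5.3 and 5.4 could place or document the first application at the site.
- **Exclusion.** The ITT wording asks for one dose and no later visit, in contrast to the PP set. A subject who applied product once and stopped because of it is in ITT by that wording. Nothing says an undocumented dose means exclusion. Section 8.3.1 also obliges the investigator to pursue adequate information on adverse events, so knowledge of an early stopper need not depend on a returned diary.
- **Counting as failures.** A rule for missing outcomes would normally sit in section 10.2.2, whose efficacy text is redacted. Its absence cannot be claimed.
- **Size and direction.** Every loss and closure count above is assumed. Ten of 125 lost by week 1 would use 40% of the 25 subjects allowed for non-evaluability of any kind. Section 4.2 makes the two creams identical, so failure to start should not differ by arm.

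All of this stands, and it limits the point to a weakness in the definition. It does not remove it. A non-responder rule in section 10.2.2 would reach only subjects already kept in the set. Identical creams do not rule out differential loss among subjects who did apply product, and these are the subjects whose dose may be undocumented.

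**Conclusion.** The point holds in a limited form, as a cheap improvement and not a demonstrated bias. The deciding set is a modified ITT, conditional on a post-randomization event that is undefined in the visible text and that, for a subject who never returns, the listed diary and product procedures cannot confirm. Whether anyone would actually be excluded depends on how receipt is read and on redacted text.

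Under the assumed counts, loss in proportion to allocation matters little (about 1 to 3.5 points for 5 to 15 exclusions). Two exclusions on vehicle alone, or four on CSTC1 alone, are enough to change significance in a borderline result. The bias can favour either arm. No figure in the plan changes.

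The mismatch between three announced sets and two defined is a separate drafting defect. That the third was meant to be a safety set is a guess, since section 10.2.1 assigns safety to ITT.

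**What to change.** In section 10.2.1 and the Protocol Summary:

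1. Define ITT as all randomized subjects, analysed in the arm assigned.
2. For the primary endpoint, count every subject without confirmed complete closure as not closed, unless section 10.2.2 already says so.
3. Move the at-least-one-dose condition to a separate safety set, analysed as treated. Define there whether a dose is received when product is dispensed or when it is applied, and say how a subject with no returned diary or product is classified.
4. Assign the safety endpoints to that set. This also brings the number of sets defined into line with the three announced.

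The cost is protocol and SAP wording. Closure rates in both arms become slightly lower: in the example with 8 and 2 early losses, CSTC1 goes from 65.2% to 60.0% and vehicle from 39.1% to 36.0%. In return, membership of the deciding set can be read from the randomization list alone.
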